The secondary endpoints include:

- Rates of achieving a critical view of safety.
- Rates of different bailout procedures initiated when safe cholecystectomy is compromised.
- 30-day and one-year rates of textbook outcomes [2] for cholecystectomy, which covers: postoperative complications (Clavien-Dindo classification), intraoperative complications (including bile duct and vascular injuries), length of stay, readmission, mortality, and postoperative imaging or intervention.
- Unsuspected gallbladder cancer rates and their 30-day and one-year outcome rates, which includes: (1) complication rates (Clavien-Dindo classification); (2) time-to-recurrence rates (time from surgery to recurrence); and (2) revisional surgery rates (liver resection, bile duct resection and/or lymph node dissection).
- A description of the global variation in the availability of cholecystectomy services, training and sustainable practice.

Control of Bias and Confounding

Data will be collected on audit standards and confounding factors for risk-adjusted analyses. These include age, sex, body mass index, American Society of Anaesthesiologists (ASA) grade, and relevant comorbidities. Variables including operative urgency, operative contamination, and operative approach will also be collected. Without appropriately adjusting for risk factors, it is likely that any findings would be biased and unable to be appropriately analysed on an international scale. A full list of required data fields is available in **Appendix B**, and on the REDCap database.

Data Analysis & Sample Size

Variation across different international health settings will be tested using the human development index (HDI) countries [17] a composite statistic of life expectancy, education and income indices published by the United Nations. Initially, data will be reported using descriptive analyses. Comparisons between groups will be undertaken using appropriate parametric and non-parametric analyses. Multilevel logistic regression multivariate models will be constructed to account for case mix, with population stratification by hospital and country as random effects.

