Operative approach	 Open (Why?  No laparoscopy  Surgeon not trained in laparoscopy  Laparoscopy broken  Previous surgeries  Disease severity)  Open conversion (Why?  Suboptimal view  Adhesions  Unable to safely dissect CVS  Suspected BDI  Pneumoperitoneum not tolerated  Bleeding  Bowel injury  Equipment failure  Suspected or actual cholecystoduodenal or cholecystocolonic fistula  Laparoscopic (Type:  Standard  SILS; Gasless?  Yes  No; Reusable equipment:  Yes  No)  Robotic (Type:  Standard  SILS; Gasless?  Yes  No; Reusable equipment:  Yes  No)							
Intraoperative difficulty (Nassar) - for minimally invasive technique	 I  II  III  IV  V	CVS obtained successfully? - for minimally invasive technique  Yes  No		If No, which criteria was met? (Tick all that apply)  Clearance of the hepatocystic triangle  Exposure of the lower cystic plate  Only two structures are attached to the gallbladder  None of the above		Was there a time-out to verify CVS?  Yes  No		

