APPENDIX B: DATA DICTIONARY

Pre-operative Data Fields	Required data (definition / comment)
1. Patient age	Years (Whole years at the time of operation)
2. Patient sex at birth	Male / Female
3. ASA grade	I / II / III / IV / V (Appendix D for definitions)
4. Body Mass Index (BMI in kg/m ²)	Underweight BMI Below 18.5 / Normal weight BMI 18.5-24.9 / Pre-obesity BMI 25.0-29.9 / Obesity class I BMI 30.0-34.9 / Obesity class II BMI 35.0-39.9 / Obesity class III BMI 40+
5. Clinical Frailty Scale	1 / 2 / 3 / 4 / 5 / 6 / 7 / 8 / 9 (Appendix D for definitions)
6. Comorbidities (Select all that apply)	
Myocardial Infraction (MI) / Congestive Heart Failure (CHF) / Peripheral Vascular Disease (PVD) Cerebrovascular Accident (CVA) or Transient Ischaemic Attack (TIA) / Dementia / Chronic Obstructive Pulmonary Disease (COPD) / Connective Tissue Disease (CTD) Peptic Ulcer Disease (PUD) / Hemiplegia / Leukaemia / Lymphoma / Human Immunodeficiency Virus (HIV) or Acquired Immunodeficiency Syndrome (AIDS) / Hypertension / Inflammatory Bowel Disease (IBD) / Diabetes Mellitus (Type 1 or Type 2). If yes: Diet-Controlled / Medication (non-insulin) controlled / Insulin-controlled Solid Tumour. If yes: Localised / Metastatic Liver Disease. If yes: Mild / Moderate to Severe Chronic Kidney Disease (CKD). If yes: Stage I / II / IIIa / IIIb / IV / V None of the Above
 
Definitions:
 
 eGFR for CKD stages: I ≥ 90; II = 60-90; IIIa = 45-59; IIIb = 30-44; IV = 15-29; V <15 Definitions for Liver Disease: Mild defined as chronic hepatitis or cirrhosis without portal hypertension; Moderate defined as cirrhosis and portal hypertension but no variceal bleeding history; Severe defined as cirrhosis and portal hypertension with variceal bleeding history.
7. History of acute cholecystitis or cholangitis	Yes / No
8. Number of admissions with biliary symptoms in previous 12 months prior to surgery	Number of admissions excluding the current one
9. Preoperative imaging (Select all that apply)	Yes / Unknown / No (Not available / Not indicated / Patient declined) for each of the following: USS / CT / ERCP / MRCP / Endoscopic Ultrasound (EUS) / Hepatobiliary IminoDiacetic Acid (HIDA)

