2. Intraoperative antibiotics*	
Yes (Prophylactic / Intraoperative spillage / Cholecystitis) / No *Defined as administration of antibiotics at least 30 minutes prior to skin incision to end of operation

3. Primary operator	
Consultant or attending Senior trainee (i.e., senior registrar or resident with >4 years surgical training/residency) Junior trainee (i.e., junior registrar or resident with ≤ 4 years surgical training/residency) Non-surgeon (e.g., medical practitioner or nurse)
 
If Consultant: What specialty? (General / Oesophago-gastric (OG) / HPB / Colorectal / Breast / Vascular / Other) If Trainee: Was this a training operation? (Yes / No). Was a consultant present? (Yes / No) If any: Number of cholecystectomies performed prior to this procedure: 0-50 / 51-100 / 101-200 / >200

4. Operative approach	
Open / Open conversion / Laparoscopic (Standard / Single Incision Laparoscopic Surgery (SILS)) / Robotic (Standard / SILS)
 
 If open, why: No laparoscopic equipment / Surgeon not trained in laparoscopy / Laparoscopy equipment broken / Multiple previous surgery / Disease severity. If open conversion, why: Suboptimal view / Adhesions / Not able to safely dissect CVS / Suspected bile duct injury / Patient unable to tolerate pneumoperitoneum / Bleeding / Bowel injury / Laparoscopic or robotic equipment failure / Suspected or actual cholecystoduodenal or cholecystocolonic fistula. If laparoscopic or robotic: was this gasless (Yes / No), were reusable equipment used? (Yes / No).
5. Intra-operative difficulty score – this is for minimally invasive surgery	
I / II / III / IV / V (Nassar Grade: Appendix D for definitions)

6. Was the Critical View of Safety (CVS) obtained (all three) – this is for minimally invasive surgery	
Yes / No If no, which criteria was met: 1) Clearing fat and fibrous tissue from the hepatocystic triangle.

	2) The lower third of the gallbladder being cleared from the cystic plate. 3) Only two structures are attached to the gallbladder.
7. Was there a time-out to verify CVS	Yes / No Defined as a momentary pause that what one is seeing is likely the correct anatomy

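### The closed list of reasons for a primary open operation has no 'Other', cost, preference or anaesthetic option, so open cases done for an unlisted reason may be miscoded or left blank (minor)

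*Protocol*

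**What the plan says.** Appendix B, intra-operative item 4 (operative approach), asks why the operation was open and gives a closed list: "No laparoscopic equipment / Surgeon not trained in laparoscopy / Laparoscopy equipment broken / Multiple previous surgery / Disease severity". The case report form in Appendix A carries the same five choices in shorter wording, for example "Surgeon not trained in laparoscopy". Neither version provides free text, and neither tells the collector to tick every reason that applies, although several other fields on the same forms do.

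The next line of item 4 gives a separate list for conversion to open, which includes "Suspected bile duct injury / Patient unable to tolerate pneumoperitoneum / Bleeding / Bowel injury". That list has no 'Other' either.

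On the standing of the dictionary, Control of Bias and Confounding says "A full list of required data fields is available in" Appendix B and on the REDCap database. Data Governance adds that the dictionary was limited to fields needed for analysis. The secondary endpoints include "A description of the global variation in the availability of cholecystectomy services, training and sustainable practice".

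**The concern.** A closed list works only if it covers the reasons that occur, or has a residual category for the rest. This one has neither an 'Other' nor an 'Unknown'. A patient operated open because laparoscopy was not affordable, because pneumoperitoneum was judged unsuitable beforehand, or because patient or surgeon preferred it has no correct code. The collector can pick the nearest wrong one or leave the item empty.

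What is at stake is the patient-level description of why minimally invasive surgery was not used. Three of the five codes concern equipment or training, so a cost or preference reason could appear as a resource barrier, or else as disease. The protocol compares settings by human development index. If unlisted reasons are more common in some of those groups than in others, the error would be uneven across the comparison. A statistical analysis plan could not repair this, because the information would never have been recorded.

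**Working it through.** No published figure is in dispute, so the check is a count of response options, a comparison with neighbouring fields, and a test of whether the completeness rules force an answer.

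**1. Count of options for a primary open operation**

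| Type of reason | Appendix B | Appendix A |
|---|---|---|
| Equipment or training | 3 | 3 |
| Patient or disease | 2 | 2 |
| Cost | 0 | 0 |
| Pneumoperitoneum or anaesthetic | 0 | 0 |
| Patient or surgeon preference | 0 | 0 |
| Other, Unknown or free text | 0 | 0 |
| Total | 5 | 5 |

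The two versions agree except in wording: the dictionary's prior-surgery option specifies multiple operations, while the form's does not.

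**2. Comparison with fields on the same forms**

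- Conversion reasons (Appendix B, item 4) include "Patient unable to tolerate pneumoperitoneum". The primary-open list has no equivalent.
- Consultant specialty (Appendix B, intra-operative item 3) ends in a residual category: "Oesophago-gastric (OG) / HPB / Colorectal / Breast / Vascular / Other". Neither reason list does.
- Pre-operative imaging (Appendix B, pre-operative item 9) divides a 'No' into "Not available / Not indicated / Patient declined" and also allows an unknown answer. Availability, clinical judgement and patient choice are thus separated there but not here.

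The designers therefore used each of these devices elsewhere. Nothing else in the protocol supplies the missing reasons for an open approach.

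**3. Do the completeness rules force a code?**

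Authorship requires more than 95% of data points per record. Study Setting excludes centres with more than 10% missing. Counting numbered items in Appendix B that apply to every patient followed to one year, with one gateway item each for bile duct injury and histology:

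15 pre-operative + 16 intra-operative + 6 thirty-day + 1 + 1 + 3 one-year = 42.

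One blank is 1/42 = 2.4% of a record, leaving 97.6% entered. That breaches neither limit. Counting sub-fields separately would enlarge the denominator and make one blank smaller still. A blank is therefore permitted. The rules discourage blanks in general but do not compel a wrong code.

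**4. Effect on the breakdown**

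Let *u* be the share of open cases with an unlisted reason and *b* the fraction of those left blank. The miscoded share is *u*(1 − *b*). The most that any one code can gain, among all open cases, is *u*(1 − *b*), reached only if every miscoded case goes to that code. If all unlisted cases are left blank (*b* = 1) and blanks are dropped from the denominator, a code with true share *p* is reported as *p*/(1 − *u*). The breakdown is therefore distorted either way. The protocol gives neither the expected proportion of open operations nor the distribution of reasons, so *u*, *b* and a patient count cannot be evaluated.

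**The case against.** The strongest reply is that this is a descriptive sub-field outside every stated endpoint. The reason for open surgery is not an audit standard, primary or secondary outcome, or prespecified subgroup; the subgroups use the approach itself. The aim on availability of services is framed at hospital level. Study Procedures assigns that description to the site survey, and Appendix C asks about access to minimally invasive equipment, the number of consultants doing laparoscopic cholecystectomy, and hospital funding. All of this stands, and it sets the severity. It does not remove the gap: a hospital-level survey cannot say why a particular patient at an equipped hospital had open surgery.

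Second, other fields give context. Mode of anaesthesia, ASA grade, frailty and comorbidities bear on anaesthetic suitability; the duct-stone indication and duct-exploration items bear on planned open duct surgery. This partly stands, but context is not a recorded reason, and nothing comparable exists for cost or preference.

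Third, the contrast with the conversion list is imperfect. Intolerance of pneumoperitoneum there is an event during an attempted minimally invasive operation, and gasless laparoscopy is eligible and recorded. That is fair. The contrast shows that the form recognises the reason, not that the two lists should be identical.

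A reader might go further and infer that the reasons for open surgery will generally be miscoded because the completeness rules force an answer. The documents do not support that. Cases with a listed reason can be coded correctly, nothing in the protocol makes this sub-field mandatory, and one blank stays inside both limits.

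**Conclusion.** The point holds as a minor defect of form design. The list is closed, has five options and no residual category, and omits reasons that the same forms recognise in other fields. Open cases done for an unlisted reason may be miscoded or left blank, and the resulting breakdown of why laparoscopy was not used would be distorted to that extent.

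No size can be put on it. A reader might be tempted to multiply the anticipated sample of about 15,000 by an assumed open share and an assumed share of unlisted reasons. Any such figure would rest wholly on those two assumptions, and to call the product 'miscoded' would also assume no blanks. It would likewise go too far to say that the availability aim is undermined, since the site survey is its main source and this field only supplements it. No sample-size figure depends on the field.

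The conclusion assumes that the REDCap form, which is not shown, has the same options as the two appendices.

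**What to change.** In both Appendix A and Appendix B, and in REDCap to match:

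- Add 'Other (specify)' to the list of reasons for a primary open operation and to the list of reasons for conversion.
- Add at least three options to the primary-open list: 'cost to patient / not funded', 'medical or anaesthetic reason against pneumoperitoneum', and 'patient or surgeon preference'.
- Mark the primary-open list 'tick all that apply'.
- Use the same wording for the prior-surgery option in both appendices.

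'Other (specify)' alone would end the forced choice. The named options keep the likelier reasons out of free text and make them countable. The cost is a few extra tick boxes in one field and a small free-text category to code. Nothing in patient care, the sample size or the endpoints changes.

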The advent of laparoscopy fundamentally evolved biliary surgery and quickly became the “gold standard” approach. Recent multicentre collaborative studies [3,4,5] have elucidated that the burden imposed on healthcare systems by laparoscopic cholecystectomies is primarily due to patient readmissions and complications arising from the operation, rather than perioperative mortality burden that was more commonly seen in open surgery [6]. As a result, national and international societies [7,8] have shifted their focus towards creating a culture of safety around this procedure, with the overarching goal of improving patient satisfaction and reducing hospital costs. Gupta et al. [9] described safe cholecystectomy as one that is “safe for both the patient (no bile duct/hollow viscus/vascular injury) and for the operating surgeon (no or minimal scope for litigation)”. The universal establishment of safe cholecystectomy is a complex process that relies not only on the operation itself, but also on various other factors such as promoting adequate training, improving hospital infrastructure, and enhancing peri-operative patient care.

There remains a paucity of evidence around the variations of safe provision of laparoscopic surgery for gallbladder disease internationally, including low- and middle-income countries. To bridge this knowledge gap, the **Global Evaluation of Cholecystectomy Knowledge and Outcomes (GECKO)** study (GlobalSurg 4) will be an international collaborative effort, delivered by the GlobalSurg network [10], that will allow contemporaneous data collection on the quality of cholecystectomies using measures covering infrastructure, care processes and outcomes. It will be disseminated via contacts from the National Institute for Health and Care Research (NIHR) Global Surgery unit, leading emergency general surgeons and specialist organisations.

Study Aims

The **primary** aim of this study is to define the global variation in compliance to pre-, intra-, and post-operative audit standards (see pages 9-10).

The **secondary** aims of this study are to:

1. To determine the quality of safe provision of cholecystectomy, including the rates of: (i) achieving a critical view of safety; (ii) intraoperative imaging use (e.g., cholangiogram); and (iii) initiating of different bailout procedures (e.g., subtotal cholecystectomy) when safe cholecystectomy is compromised.

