Operation performed	 Total cholecystectomy (Type:  Standard  Fundus-first approach)  Subtotal cholecystectomy (Type:  Reconstituting  Fenestrated)  Not performed ( Diagnostic laparoscopy  Cholecystostomy)		Abdominal drain  Yes  No		Anatomical biliary variant  Yes  No			
Intraoperative CBD assessment (Tick all that apply)	 Intraoperative cholangiogram  Incisionless fluorescent cholangiography  Laparoscopic US  Intraoperative ERCP Decision:  Selective  Routine; If selective, indication:  Raised LFT  BDI concern  Pre-op imaging suggests CBD stone Findings:  Stone  No stone; If stone, management:  Flushing with saline and smooth muscle relaxant  Fogarty catheter trawl  Basket retrieval  Choledochoscope  No intraoperative treatment attempted							
CBD exploration	 Yes (Type:  Trancystic  Choledochotomy; If Choledochotomy, closure:  Primary closure  T-tube)  No		Operative contamination  Clean  Clean-Contaminated  Contaminated  Dirty					
Intraoperative complications - excluding BDI (see section 4)	 Bile spill  Stones Spilt  Bleeding  Major vascular injury  Bowel injury		Reusable gowns  Yes ( All staff  some staff)  No		Reusable drapes  Yes  No			
Section 3: 30-day outcomes								

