8. Operation performed	Standard total cholecystectomy Total cholecystectomy by the fundus-first (top down) approach Subtotal cholecystectomy (reconstituting / fenestrated) Not performed (diagnostic laparoscopy / cholecystostomy) Definitions of subtotal cholecystectomy: 
 Fenestrated: does not occlude the gallbladder but may suture the cystic duct internally Reconstituting: closes off the lower end of the gallbladder, creating a remnant gallbladder
9. Abdominal drain insertion	Yes / No
10. Anatomical Biliary variant	Yes / No
11. Intraoperative CBD Assessment	Intraoperative cholangiogram (IOC) / Incisionless fluorescent cholangiography/ Laparoscopic ultrasound / Intraoperative ERCP If yes to any of the above: 
 Decision: Selective / Routine. If selective, state Indication: Raised liver function test / Concern of a bile duct injury / pre-operative imaging suggestive of CBD stone Findings: Stone / No stone. If stone, tick all that apply for management: Flushing with saline and smooth muscle relaxant / Fogarty catheter trawl / Basket retrieval / Choledochoscope / No intraoperative treatment attempted
12. Common Bile Duct exploration	Yes (Trancystic / Choledochotomy) / No If Choledochotomy then select closure: Primary closure / T-tube
13. Operative contamination	Clean (Gastrointestinal (GI) and genitourinary (GU) tract not entered) Clean-Contaminated (GI or GU tracts entered but no gross contamination) Contaminated (GI or GU tracts entered with gross spillage or major break in sterile technique) Dirty (There is already contamination prior to operation, e.g., faeces or bile).
14. Intraoperative complications - excluding bile duct injury (BDI) (Select all that apply)	Bile spilt / Stones Spilt / Bleeding / Major vascular injury / Bowel injury
15. Were reusable gowns used in this procedure?	Yes (All scrubbed staff/ some scrubbed staff) / No
16. Were reusable drapes used in this procedure?	Yes / No
30-day Outcomes	Required data (definition / comment)
1. Highest 30-day Clavien-Dindo (CD) Grade	0 / I / II / IIIa / IIIb / IVa / IVb / V (Appendix D for definitions) If CD IIIa: Radiological drainage (yes / No) If CD IIIb: Re-laparoscopy (yes / No) If CD V (death): please indicate time from index cholecystectomy to death: number of days (whole number, 0 = same day)

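### The printed fields for intraoperative imaging and non-BDI intraoperative complications have no negative option, and the protocol does not say whether a blank means negative or missing

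*Protocol*

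**What the plan says.** Appendix B, intra-operative item 11 (intraoperative CBD assessment) gives four modalities: "Intraoperative cholangiogram (IOC) / Incisionless fluorescent cholangiography/ Laparoscopic ultrasound / Intraoperative ERCP". The sub-questions on decision, indication and findings open under "If yes to any of the above". Section 2 of the CRF in Appendix A prints the same field as "Intraoperative CBD assessment (Tick all that apply"), with four boxes.

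Appendix B item 14 (intraoperative complications other than bile duct injury) gives "Bile spilt / Stones Spilt / Bleeding / Major vascular injury / Bowel injury", with all that apply to be selected. The CRF heads it "Intraoperative complications - excluding BDI (see section 4") and prints five boxes.

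Neither field, in either appendix, has an entry for none, no or unknown.

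Both fields feed named outcomes. Study Aims, secondary aim 1, includes the rate of "intraoperative imaging use (e.g., cholangiogram"). Intraoperative imaging is also one of the intra-operative audit standards, and compliance with those standards is the primary endpoint. Under Secondary Outcome Measures, the textbook outcome covers "intraoperative complications (including bile duct and vascular injuries").

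There are two completeness rules. Study Setting excludes a centre with more than 10% missing data, counted over all data points. Authorship requires more than 95% of data points entered per record.

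**The concern.** For both fields the negative answer carries as much information as the positive one, and a positive-only tick-list records it as an absence of ink. A patient who had no imaging and a patient whose imaging question was overlooked produce identical records.

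What is at stake is the imaging-use rate, the imaging audit standard and the non-BDI complication component of the textbook outcome. The study compares these across health settings. If the share of overlooked fields differs between settings, part of any difference in the results would reflect form completion and not surgical practice. An analysis plan can choose how to read a blank, but it cannot recover a distinction that the form did not record.

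**Working it through.** **1. The option lists side by side (Appendices A and B).**

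| Field | Explicit negative printed? |
|---|---|
| Comorbidities | Yes: "None of the Above" |
| CVS criteria met, if CVS not achieved | Yes on the CRF; not in the dictionary |
| Preoperative imaging | Yes: yes, unknown, or no with a reason, for each modality |
| Imaging to confirm BDI | Yes: a none option |
| Drain, biliary variant, CBD exploration | Yes: Yes/No |
| 30-day complications | None box absent, but the companion field (highest Clavien-Dindo grade) includes 0 |
| Item 11, intraoperative CBD assessment | No, and no companion field |
| Item 14, intraoperative complications | No, and no companion field |

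**2. If a blank is read as negative.** Let p be the true rate and m the share of records in which the field was skipped. Then observed rate = p × (1 − m). The documents give neither p nor m, so both are assumed and shown over a range.

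| True p | m = 2% | m = 5% | m = 10% | m = 20% |
|---|---|---|---|---|
| 10% | 9.8% | 9.5% | 9.0% | 8.0% |
| 20% | 19.6% | 19.0% | 18.0% | 16.0% |
| 30% | 29.4% | 28.5% | 27.0% | 24.0% |

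The relative under-count equals m. Two settings with the same true 30%, one skipping 2% and the other 20%, would show 29.4% and 24.0%. That is a gap of 5.4 percentage points produced by form completion alone. For the textbook outcome, a complication lost in this way can raise the rate and cannot lower it.

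**3. If a blank is read as missing.** On the printed lists every non-blank record is a positive, so a rate computed among completed records is p(1 − m) / p(1 − m) = 100%. That is not usable as an estimate. True negatives also count as incomplete. Take one data point per top-level dictionary item: 15 pre-operative + 16 intra-operative + 6 at 30 days + 1 BDI lead item + 1 histology lead item + 3 at one year = 42. This count is an assumption, because the protocol does not define a data point. A fully documented patient with no imaging and no complication then scores 40/42 = 95.2%. One further gap gives 39/42 = 92.9%, below the 95% authorship rule. At centre level, up to 2/42 = 4.8 percentage points of the 10% allowance would go on correct data.

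**4. Whether the completeness rules would catch skipping.** Suppose blanks count as missing and a centre leaves both fields blank in every record. Completeness is 1 − 2/T:

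- T = 39 (three items not applicable to every patient): 94.9%
- T = 42: 95.2%
- T = 80: 97.5%

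All three pass the 90% rule. The 95% rule is passed whenever 2/T < 0.05, that is T > 40. If blanks count as complete, the rules do not see these fields at all.

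**The case against.** The strongest reply is that the printed form is not the database. Data Governance encourages direct entry into REDCap, Control of Bias and Confounding says the full field list is also held there, and the print is not exhaustive: the none option for the CVS criteria is on the CRF but not in the dictionary. The wording "If yes to any of the above" would fit a yes/no prompt per modality. This stands as a possibility, but neither appendix shows such a prompt, and paper forms are permitted.

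A reader might go further than the documents allow in three ways.

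- **That a skipped field is scored as negative.** Step 3 makes this tempting, since the other reading gives no usable rate. But no section sets a scoring rule, and handling of blanks may properly sit in a statistical analysis plan that was not available here.
- **That 10% is a tolerated skip rate for these fields.** The Study Setting threshold is per centre over all data points. It is neither a field-level tolerance nor an upper bound on m.
- **That the loss is undetectable.** Independent validators re-collect two operation variables (Data Validation), though which two is not stated. The site survey asks whether cholangiography, laparoscopic ultrasound and ICG are used routinely or selectively, so blank item 11 entries at a routine-use site would stand out. Antibiotics given for spillage, contamination class and reasons for conversion partly cross-check item 14. These checks are real but incomplete.

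It is also fair to say that other lists, such as preoperative imaging findings and staging investigations, print no negative option. Items 11 and 14 are singled out because they feed named aims and endpoints and have no companion field that records the negative.

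**Conclusion.** The concern holds in a limited form. As printed in both appendices, items 11 and 14 cannot separate a true negative from an omission, comparable fields on the same form can, and the protocol does not say which reading applies. The consequence depends on that reading. Either the imaging-use and non-BDI complication rates are under-counted by the relative share m, or true negatives are counted as missing under rules that in any case do not protect a single field.

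The size is unknown, because the documents give no skip rate. The tables rest on assumed rates, and the completeness figures on an assumed count of about 42 data points. That skipping is worse in particular settings is also an assumption. Ascertainment of bile duct injury is not affected: item 14 excludes it, and it has its own Yes/No question at 30 days and one year.

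**What to change.** In the CRF, the data dictionary and REDCap, add a none-performed option to item 11 and a none option to item 14, ideally with unknown as well, and require one selection in each. Then state that a record with no selection is missing, both in the imaging-use and textbook-outcome analyses and in the completeness count. The order matters: the missing-data rule works only once the negative option exists. If REDCap already has such an option, printing it in both appendices and stating the rule is enough.

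For any records already entered on the positive-only lists, report the number of blanks, state how they were read, and describe rates that read blanks as negative as possible under-counts.

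The cost is a few extra boxes to tick. No new information has to be found.
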